^a Hespan (6% HES 450/0.7 in 0.9% Sodium Chloride Injection) is not recommended for use as a cardiac bypass pump prime, while the patient is on cardiopulmonary bypass, or in the immediate period after the pump has been discontinued because of the risk of increasing coagulation abnormalities and bleeding in patients whose coagulation status is already impaired.

- 3) **Secondary Aim 2: Safety assessment (coagulation and platelet function).** To assess the safety of HES 130/0.4 versus albumin 5% as measured by coagulation parameters and platelet function measured at baseline, within one hour of arrival to ICU (\pm 1 hour), and 24 hours (\pm 2 hours) following surgery (or within two hours prior to discharge from the ICU if patient is discharged in less than 24 hours). Additional exploratory clinical outcomes including blood loss and transfusion requirements will also be collected.
- 4) **Tertiary Aim 1: Exploratory analyses (inflammatory response).** To assess the anti-inflammatory effects of intraoperative administration of HES 130/0.4 in cardiac surgical patients measured by perioperative levels of interleukin - 6 (IL-6), tumor necrosis factor - α (TNF- α), and macrophage migration inhibitory factor (MIF), measured at baseline (following anesthetic induction and prior to surgical incision), within one hour of arrival to ICU (\pm 1 hour), and 24 hours (\pm 2 hours) postoperatively (or within two hours prior to discharge from the ICU if patient is discharged in less than 24 hours) compared with patients who received 5% human albumin.
- 5) **Tertiary Aim 2: Exploratory analysis (pulmonary function).** To examine whether intraoperative administration of HES 130/0.4 compared with 5% albumin affords benefit on postoperative pulmonary dysfunction as measured by ratio of partial arterial oxygen tension (PaO₂) to fraction of inspired oxygen (FiO₂) measured at baseline, within one hour of arrival to ICU (\pm 1 hour), and 6 hours following ICU arrival (\pm 1 hour) or within 30 min prior to initiation of Continuous Positive Airway Pressure (CPAP) weaning trial prior to extubation , whichever is earlier. Additional exploratory outcome measures including dynamic lung compliance will be assessed.

The Effects of 6% HES 130/0.4 in Cardiac Surgical Patients

BACKGROUND

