Recently, new generation HES solutions, such as HES 130/0.4 with lower molecular weight and molar substitution, have been purported to have minimal adverse effects on coagulation parameters.^{15,16} A pooled analysis which compared HES 130/0.4 with earlier generation HES found that HES 130/0.4 produced less abnormalities in coagulation, less blood loss and lower transfusion requirements compared with the earlier generation HES solutions.¹⁷ In addition, newer HES solutions have been found to inhibit the inflammatory response, which may further decrease risk of postoperative coagulopathy. However, although some investigations of the coagulation effects of HES 130/0.4 in cardiac surgical patients found minimal effect on coagulation parameters,¹⁵ conflicting evidence exists.¹⁸ Some reports found that HES 130/0.4 caused global extrinsic and intrinsic pathway coagulation abnormalities in contrast to albumin.¹⁸ In addition, a large randomized controlled trial found that HES 130/0.42 (Tetraspan) was associated with increased incidence of severe bleeding in septic critically ill patients.² Further, a recent meta-analysis of 18 randomized, controlled trials found increased risk of bleeding, blood product transfusion, and reoperation in patients who received HES solutions during cardiac surgery.⁸ This report was limited, however, by the fact that head-to-head trials comparing risk of bleeding of newer generation HES solutions, such as HES 130/0.4 with human albumin 5% have not been performed. In fact, the analysis extrapolated results from older generation HES solutions (HES 200/0.5) to the newer HES products, because no direct comparison was available. Nevertheless, because of these recent results, the FDA has added safety information, specifically, the risk of excess bleeding in cardiac surgical patients, to the Warnings and Precautions section

of the package insert of all HES products,^b irrespective of molecular weight or degree of molar substitution. Thus an investigation comparing coagulation abnormalities and bleeding between albumin and the newer HES products, namely HES 130/0.4 (Voluven) are necessary to examine the safety profile in cardiac surgical patients.

Thus, whether HES 130/0.4 (Voluven) impairs clinical and laboratory coagulation parameters compared to albumin in adult cardiac surgical patients is unclear and the clinical impact is unknown. Further investigation of the safety of HES 130/0.4 administration on coagulation parameters is needed.

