- 2) Additional coagulation measures from thromboelastography, including the **reaction time (R value)**, **clot formation time (K value)**, **angle (α)**, **maximum amplitude (MA)**, **clot lysis at 30 min (LY30)**. We will collect data on **coagulation index (CI)** and compare between groups, because it is a clinically important measurement. However, the CI is based on the components of thromboelastography (a summary variable); thus it will not be included as an outcome measure.
- 3) Assessment of **platelet function**, including platelet count, **ADP-, collagen- and arachidonic acid platelet aggregation**

Descriptive variables of transfusion, coagulation and platelet function)

- 1) Amount of cell saver administration, packed red blood cell administration, fresh frozen plasma, and platelets transfused, chest tube output during surgery and in the first 24 hours following surgery (or until ICU discharge, if the patient is discharged in less than 24 hours).
- 2) We will store blood samples for later analysis for coagulation and platelet function, possibly including measures of Factor VIII, von Willebrand's factor, thrombin time, fibrinogen, D-dimer.

Tertiary Outcome Measures

Tertiary aim #1 (exploratory analysis, inflammatory response)

To compare whether intraoperative administration of HES 130/0.4 (Voluven) versus human albumin 5% affords beneficial anti-inflammatory effects as measured by an important markers of the perioperative inflammatory response.

The **tertiary outcomes** will include serum concentrations of **IL-6, TNF- α and MIF**, important **markers of the inflammatory response**, to be measured at baseline, within one hour of arrival to ICU (\pm 1 hour), and 24 hours (\pm 2 hours) following completion of surgery (or within two hours prior to ICU discharge, if the patient is discharged in less than 24 hours).

Tertiary aim #2 (exploratory analysis, pulmonary function)

To compare whether intraoperative administration of HES 130/0.4 (Voluven) versus human albumin 5% provides beneficial effects on **postoperative pulmonary function** as measured by the **ratio of partial arterial oxygen tension (PaO₂) to fraction of inspired oxygen (FiO₂)**

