On arrival to the intensive care unit, lactated Ringer's solution will be administered postoperatively when the patient demonstrates signs of hypovolemia as described above. Crystallloid fluid may be given as necessary to maintain urine output exceeding 0.5 ml/h per kg ideal body weight. Postoperative pain relief will be maintained in the intensive care unit with intravenous opioids (e.g. fentanyl, morphine). Patients will be weaned from mechanical ventilation and extubated when they fulfill usual criteria that indicate the ability to maintain a patent airway with adequate ventilation and oxygenation. These criteria include an awake, alert, and oriented patient who demonstrates adequate muscle strength with sufficient respiratory mechanics (adequate tidal

volume, respiratory rate). Following tracheal extubation, patients will be given supplemental oxygen via nasal prongs or face mask to maintain oxygen saturation at greater than 92%. Postoperative nausea and vomiting may be treated with intravenous ondansetron 4 mg.

Discharge from the intensive care unit will be determined by the attending intensivist and surgeon, with consideration of the clinical condition of the patient. In all cases, good clinical judgment will predominate and the attending anesthesiologist will modify the protocol as necessary to provide optimal and safe care of the patient.

Definition of time points of laboratory assessment

“Baseline”: Baseline urine measurements will occur in the operating room following anesthesia induction and prior to surgical incision and serve as the baseline for comparison of later time points. However, preoperative laboratory blood measurements (e.g., creatinine, coagulation parameters, and other laboratory measurements) that are collected within six weeks of surgery may be used as baseline measurements – with one exception in patients who demonstrate the clinical effect of an anticoagulant agent at the time of laboratory testing. If a patient is treated with anticoagulant medication on day of laboratory testing, coagulation and platelet tests will need to be repeated on day of surgery.

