In Secondary Aim 1 – **kidney function** – we will assess noninferiority of HES to albumin on each of urinary concentration of II-18 and acute kidney injury as classified by RIFLE criteria, using statistical methods reported below under continuous (urinary concentration of II-18) and ordinal (RIFLE criteria) outcomes. These will be 1-tailed tests for noninferiority, using a noninferiority delta of 15% of the mean (or a ratio of geometric means of 1.15, if data are found to be log-normally distributed) for urinary concentration of II-18 and a noninferiority delta of 1.15 for the odds ratio assessing the effect of HES 130/0.04 on the ordinal RIFLE outcome. The noninferiority delta of 1.15 corresponds to a 15% higher odds of having a worse RIFLE score with HES 130/0.04 versus standard, and is roughly analogous to the 15% difference utilized for the continuous outcomes (urinary NGAL and II-18). A Bonferroni correction will be made to preserve alpha at 0.025 for this aim.

In Secondary Aim 2, the safety outcomes of **coagulation and platelet function** each comprise a set of several variables. Noninferiority of HES to albumin will be assessed for each outcome at the 0.025 level using a noninferiority delta of 15% of the mean (as explained above). We will claim noninferiority of HES to standard within a set if noninferiority is shown on all of the variables in a set. Therefore, no adjustment for multiple testing within a set will be done (i.e., intersection-union test).

Safety conclusions will be based on descriptive statistics as well as statistical tests. Multivariate analyses considering a vector or set of related outcomes may also be performed.

For tertiary aims all comparisons will be 2-tailed tests for superiority and analyses will follow the methods outlined below based on type of outcome variable. Each test will be conducted at the 0.05 significance level since these are exploratory analyses.

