Time to event outcomes. Randomized groups will be compared on time to event outcomes including duration of mechanical ventilation, duration of stay in the intensive care unit, and duration of hospital stay using Cox proportional hazards regression models adjusting for any baseline imbalances covariables. For these models the outcome will be time to experiencing the event while alive, i.e., time to removing the ventilator, discharge from the ICU and discharge from the hospital. Patients who die before the event occurs will be listed as failures (i.e., no event) and censored at a time just beyond the last observed event for any patient. Ignoring the deaths or censoring at the time of death may introduce bias.

Binary outcomes. Groups will be compared on binary outcomes, including in-hospital cardiac, renal, infection, or neurologic morbidity, and overall major morbidity (including death), using either logistic regression (to adjust for baseline imbalance as needed) or Pearson chi-square or Fisher's exact test, as appropriate. However, the study is not powered for assessing binary outcomes, and these analyses particularly will be interpreted with caution (whether significant or not).

For all analyses, confidence intervals for the estimated treatment effect will be provided, and these, along with the point estimates of treatment effect, will be emphasized in our reporting. SAS statistical software (Carey, NC) and R software version 2.8.1 for Windows (The R Foundation for Statistical Computing, Vienna, Austria) will be used for all statistical analyses.

Missing data. If primary or secondary outcome data are missing we will use multiple imputation of outcome values based on all available data before the time point of interest. As a secondary analysis we will conservatively assign the worst observed value for the given time point across all patients to an HES patient and best observed value to a control patient. If there is a non-trivial amount of missing outcome data we will also conduct sensitivity analyses on various forms of imputation (from none at all to full multiple imputation). However, we will work hard to avoid missing outcome data. If baseline data not included in the analyses are missing we will simply describe the missingness.

Sensitivity analyses. We will conduct a sensitivity analysis for the primary outcome that adjusts for time on CPB, length of surgery and intraoperative hypothermia.

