7. Evidence of Coagulopathy or major bleeding (worsening of parameters of coagulation function from thromboelastometry (including the reaction time (R value), clot formation time (K value), **angle (α)**, maximum amplitude (MA), **clot lysis at 30 min (LY30)**, and coagulation index (CI) and platelet function and platelet aggregometry including platelet count, ADP-, collagen- and arachidonic acid platelet aggregation), increase in serum coagulation parameters including serum prothrombin time (PT), international normalized ratio (INR), and activated partial thromboplastin time (aPTT),

8. Evidence of liver dysfunction
9. Evidence of anaphylactoid and hypersensitivity reactions
10. Serious Adverse events

Procedures for Communicating Recommendations to the Steering Committee

Executive Committee recommendations that are voted on and passed are transmitted in writing to [name]. Chair of the Steering Committee, within three working days (or less if considered urgent) of the meeting/call at which the recommendation was formulated and passed. (Figure 2)

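### Postoperative chest tube output and transfusion totals stop at ICU discharge for patients who leave before 24 hours, so the descriptive bleeding comparison covers unequal observation times

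*Combined protocol and SAP*

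**What the plan says.** Item 1 of the descriptive variables of transfusion, coagulation and platelet function lists "Amount of cell saver administration, packed red blood cell administration, fresh frozen plasma, and platelets transfused, chest tube output during surgery" and then "in the first 24 hours following surgery (or until ICU discharge, if the patient is discharged in less than 24 hours"). I read the window as applying to the whole list. In Table 1, chest tube bleeding is marked only in the 24 Hour ICU column, and cell saver only in the OR column.

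Secondary Aim 2 gives these variables exploratory status: "Additional exploratory clinical outcomes including blood loss and transfusion requirements will also be collected". They have no margin, test or power. Statistical Methods nevertheless states, after the Secondary Aim 2 paragraph: "Safety conclusions will be based on descriptive statistics as well as statistical tests".

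On what ends the window, Postoperative Management says: "Discharge from the intensive care unit will be determined by the attending intensivist and surgeon, with consideration of the clinical condition of the patient". Under Time to event outcomes, the groups are compared on "duration of mechanical ventilation, duration of stay in the intensive care unit, and duration of hospital stay using Cox proportional hazards regression models".

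No section completes the total after transfer to the ward, accounts for hours observed, or plans a fixed-window analysis. The imputation rule under Missing data covers primary and secondary outcomes. The one named sensitivity analysis concerns the primary outcome and adjusts for bypass time, surgery length and hypothermia.

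**The concern.** A cumulative amount depends on how long it is accumulated. Anything drained or transfused on the ward between ICU discharge and 24 h is left out. The cut-off depends on recovery after randomization, and the plan itself analyses ICU stay as an outcome.

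Two opposite distortions are possible. If one fluid leads to earlier ICU discharge, fewer of its hours are counted and an excess of bleeding is masked. If bleeding delays discharge, heavier bleeders are counted for longer and a true difference is exaggerated.

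Bleeding is one of the reasons for studying this product. The Background cites a meta-analysis that found "increased risk of bleeding, blood product transfusion, and reoperation in patients who received HES solutions during cardiac surgery", and says the FDA added safety information as a result. The Executive Committee report may include "Evidence of Coagulopathy or major bleeding", although that item goes on to list laboratory measures and does not define major bleeding. The item 1 totals are the trial's measured amounts of blood loss and transfusion.

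The early cut-off makes sense for blood and urine samples, because the definition of the 24-hour time point ties them to removal of lines and the urinary catheter. It is not needed for charted transfusions and drainage, since the medical record is already a data source.

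**Working it through.** **Figures in the documents.** None is given for blood loss or transfusion: no mean, SD, share of patients leaving the ICU before 24 h, or discharge time. There is nothing to reproduce, and what follows is illustration.

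**Assumed inputs.** Discharge at hour T (12 or 16, with 18 used once below). Postoperative drainage is either constant or declines with a half-time h of 12 or 6 hours. Early leavers bleed like other patients.

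**Share of the postoperative 24 h amount that is counted.** With a constant rate, f = T/24. With a declining rate, f = (1 − 2^(−T/h)) / (1 − 2^(−24/h)).

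| Leaves at | Constant | h = 12 | h = 6 |
|---|---|---|---|
| 12 h | 0.500 | 0.667 | 0.800 |
| 16 h | 0.667 | 0.804 | 0.899 |

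For example, at 16 h with h = 12: (1 − 0.397)/(1 − 0.25) = 0.804. The loss 1 − f is therefore 10–33% at 16 h and 20–50% at 12 h.

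**Spurious difference when true bleeding is equal.** If a share p of an arm leaves early, its counted mean is M × (1 − p(1 − f)), where M is the true postoperative mean. The arms then differ by M × (p1 − p2) × (1 − f). For discharge at 16 h:

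- 50% versus 20% leaving early: 0.30 × 0.101 = 0.030 up to 0.30 × 0.333 = 0.100, or about 3–10% of M.
- A 10-point gap: 0.10 × 0.101 = 0.010 up to 0.10 × 0.333 = 0.033, or about 1–3% of M.

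**Effect on a true excess.** The observed HES/albumin ratio is R × (1 − pH(1 − f)) / (1 − pA(1 − f)), where R is the true ratio and pH and pA are the shares leaving early. Take R = 1.15 as an illustration:

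| Curve and discharge time | 30% albumin, 50% HES leave early | 50% albumin, 30% HES leave early |
|---|---|---|
| h = 12, 18 h (f = 0.862) | 1.12 | 1.18 |
| h = 12, 12 h (f = 0.667) | 1.07 | 1.24 |
| Constant, 12 h (f = 0.500) | 1.02 | 1.30 |

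For the last row, left: 1.15 × 0.75/0.85 = 1.015.

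**Boundary cases.** If pH = pA, discharge times are the same and discharge is unrelated to bleeding, the ratio equals R and the arms are compared without bias, although both totals are understated. With a common 24 h window, f = 1 and the ratio equals R whatever the discharge pattern.

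**Dividing by hours observed.** With declining drainage, a rate per observed hour overstates early leavers. At 16 h it is (0.804/16)/(1/24) = 1.21 times the true 24 h rate for h = 12, and (0.899/16)/(1/24) = 1.35 times for h = 6. It replaces a 10–20% understatement with a 21–35% overstatement.

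**The case against.** The strongest reply is that little hangs on these variables and the bias may be small.

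- They are descriptive and untested. The NGAL analysis and the noninferiority tests of coagulation and platelet function do not use them. This stands and limits the severity. It does not dispose of the point, because the plan draws safety conclusions partly from descriptive statistics.
- Study fluid is given only during surgery, and both arms receive lactated Ringer's solution in the ICU. The expected benefit on ventilation is an exploratory hypothesis. A large gap in early discharge is therefore not established, and the 50% versus 20% split has no basis in the documents.
- Because discharge takes account of clinical condition, patients still draining or being transfused are less likely to leave early. The constant-rate losses probably overstate what early leavers lose. The same fact, however, links observation time to bleeding.
- Intraoperative amounts are never truncated, so every percentage above applies only to the postoperative part.
- Random error may be larger. With 65 per arm (130/2) and an assumed CV of 50–100%, the standard error of the difference is CV × √(2/65), or 9–18% of the mean. The illustrated bias is about one standard error or less, but unlike random error it does not average out.

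A reader might also infer that the trial cannot tell less bleeding from fewer hours counted, or that it has no other clinical evidence on bleeding. The documents support neither. ICU stay is collected (in days) and compared by arm, so a difference in discharge would be at least partly visible. Chest re-exploration is collected during hospitalization without the ICU cut-off.

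**Conclusion.** The point holds as a minor one. The written window gives unequal observation times for cumulative postoperative amounts. It ends at a post-randomization event, and nothing in the plan corrects for this. The resulting bias can go either way, and it is absent between arms if early discharge is equal and unrelated to bleeding.

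The illustrated 3–10% rests wholly on the assumed drainage curves, a 16 h discharge and a 50% versus 20% split. A 10-point gap gives about 1–3%.

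It may be tempting to conclude that the rule makes HES look safer, or that it undermines the trial's main result. The documents give no discharge data from which to infer a direction, and the primary and formal secondary analyses are unaffected.

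**What to change.** In item 1 of the descriptive variables of transfusion, and in the matching chest tube row of Table 1, delete the ICU-discharge cut-off for these amounts. Record chest tube output and blood products to a fixed 24 h after surgery for every patient from the medical record, including ward charting. Report hours observed by arm.

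Where ward output cannot be retrieved, flag the total as incomplete, or compare the arms over a shorter common window that all patients complete. Do not substitute mL per observed hour, for the reason shown in the working. Chest tube output still depends on a drain being in place, so a fixed clock removes the ICU cut-off but not that dependence.

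The cost is slightly more chart abstraction for patients who leave early, with no new procedure. Drainage may be charted less often on the ward than in the ICU.

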Patients will be randomized into either the HES 130/0.4 (HES) or standard care group (human albumin 5%) prior to induction of anesthesia (see Randomization above). The study drug (HES 130/0.4 (Voluven) or human albumin 5%) will be delivered to the operating room in similar

packaging and covered with a shroud to conceal the appearance of the solution (see Blinding and Unblinding above).

Intraoperative Fluid Management

On arrival to the operating room, a large-bore intravenous catheter will be inserted. Routine administration of crystalloid fluids will occur throughout the intraoperative period as a continuous infusion to provide carrier solutions for intravenous drugs, inotropic and vasopressor agents, and continuous flow to maintain patency of intravascular catheters. This routine crystalloid administration will consist of approximately one liter of fluid prior to initiation of cardiopulmonary bypass and one to two liters of crystalloid following cardiopulmonary bypass.

Following separation from cardiopulmonary bypass, the patient will be continuously monitored for acute hypovolemia requiring plasma volume replacement. Plasma volume replacement using 250 mL increments of the blinded study drug (HES 130/0.4 or 5% human albumin in similar containers and covered by a shroud) will be administered when indicated by any of the following clinical conditions (Figure 1): 1) the cardiac output/cardiac index experiences a 20% decrease from baseline; 2) the heart rate increases to 20% above baseline; 3) mean or systolic blood pressure decreases 20% from baseline; 4) a 20% increase in vasopressor requirement occurs; 5) a 20% decrease in cardiac filling pressures (central venous pressure, pulmonary artery diastolic pressures). When these conditions are met, the patient will receive 250 – 500 mL of study solution (HES 130/0.4 or 5% human albumin) as a fluid bolus. These parameters will be assessed on a continuous basis during the intraoperative period and the patient will receive the study solution each time these conditions are met. We anticipate that an average patient will receive approximately 750 – 1000 mL study solution during a routine cardiac surgical procedure.

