Fluid challenges may be repeated until no further increase in these parameters occurs, suggesting that fluid resuscitation has been successful and euvolemia has been achieved. Also, patients will receive fluid equivalent to that judged to be lost from surgical hemorrhage. The maximum dose of HES 130/0.4 will be 35 mL/kg/day. If further plasma volume expansion is needed, lactated Ringer's solution will be used for additional fluid boluses as required.

Transfusion of packed red blood cells and blood components

Minimum hematocrit (HCT) will be approximately 23% following cardiopulmonary bypass and 21% on cardiopulmonary bypass. If the HCT decreases below these values, packed red blood cell transfusions may be administered. Erythrocyte transfusions may be administered for hypovolemia in the setting of a low hematocrit (hematocrit < 26%) or if considered necessary by the attending anesthesiologist or surgeon. Platelets may be transfused for post-CPB clinical bleeding and/or platelet count < 100 after activated clotting time is normalized. Fresh frozen plasma and/or cryoprecipitate transfusion may occur if coagulopathy or severe clinical bleeding persists following protamine administration without evidence for usual hemostatic response, elevated prothrombin time, or elevated activated partial thromboplastin time. In addition, administration of blood component transfusion may be used in the clinical setting of coagulopathy or nonsurgical bleeding as determined by the attending surgeon and/or anesthesiologist.

Anesthetic and surgical management

Anesthetic and surgical patient care will be performed following usual Cleveland Clinic procedures, which include the use of standard ASA monitors, an arterial catheter, and a central venous or pulmonary artery catheter, and transesophageal echocardiography. Intravenous anesthetic induction may consist of etomidate or propofol with succinylcholine or a non-depolarizing muscle relaxant to facilitate tracheal intubation. Isoflurane, fentanyl, and/or midazolam will be administered for maintenance of anesthesia. Additional non-depolarizing muscle relaxant will be administered in incremental doses as clinically indicated. Patients who

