The randomized HES and standard therapy groups will be descriptively compared for balance on potentially confounding baseline variables (including duration of cardiopulmonary bypass, use of anti-fibrinolytic therapy, preoperative anticoagulant medications, including clopidogrel). Any baseline variable for which the standardized difference (i.e., observed difference in means or proportions divided by the pooled standard deviation of the outcome) is greater than 0.25 will be considered imbalanced and adjusted for as a covariate in each of the below analyses. We will not use P-values to determine baseline imbalance since the P-value is quite dependent on the sample size, whereas the standardized difference is more independent of sample size and thus a better assessment of balance. [A standardized difference of 0.25 is conservative (should be 0.39) based on the expected 2.5th and 97.5th percentiles of the sampling distribution, i.e., $1.96 \times \sqrt{2/n}$ per group = 50 = 0.39.]³⁰ For all analyses of continuous variables, transformations of the data will be made as appropriate to achieve normality and/or meet other model assumptions. If transformations are not successful, non-parametric analyses analogous to those described below will be employed. For example, we might employ a Wilcoxon rank-sum test to compare the groups on IL-6 at a particular time point if the data are not close to a normal or log-normal distribution.

All primary analyses will be modified intent-to-treat (M-ITT), such that the groups being compared will be all patients who are randomized and who undergo surgery. Analyses of the safety outcomes in Aims 1 and 2 will be noninferiority assessments, and so 1-tailed. All tertiary analyses will be 2-tailed tests for superiority. Conclusions about the effect of HES will be confirmatory for the primary outcome (urinary NGAL) and more exploratory for other outcomes. We will also conduct a “per protocol” analysis for the primary outcome and describe whether these results differ from the modified intent-to-treat results. In the per-protocol analysis we will analyze patients according to the treatment received as oppose to the randomized treatment, and only those patients who complete the entire trial according to the protocol will be included. In case of a discrepancy, the M-ITT results will be primary.

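### Every post-baseline coagulation and platelet sample in Secondary Aim 2 follows the period in which blood components may be given, and the plan has no rule for values measured after transfusion

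*Combined protocol and SAP*

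**What the plan says.** All references are to the combined protocol and SAP.

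- **Study fluid** (Intraoperative Fluid Management): "Following separation from cardiopulmonary bypass, the patient will be continuously monitored for acute hypovolemia requiring plasma volume replacement". Boluses of blinded HES or albumin are given in that period.
- **Components** (Transfusion of packed red blood cells and blood components): "Platelets may be transfused for post-CPB clinical bleeding and/or platelet count < 100 after activated clotting time is normalized". Plasma or cryoprecipitate may follow protamine if coagulopathy or severe bleeding persists, with the qualifying words "without evidence for usual hemostatic response, elevated prothrombin time, or elevated activated partial thromboplastin time". The attending surgeon or anesthesiologist may also order components on judgment.
- **Samples** (Secondary outcome measures 2; Definition of time points of laboratory assessment; Table 1): baseline, around ICU arrival after surgery is complete, and 24 hours or shortly before an earlier ICU discharge.
- **Transfusion data** (descriptive variables of transfusion, coagulation and platelet function): "Amount of cell saver administration, packed red blood cell administration, fresh frozen plasma, and platelets transfused", with chest tube output, during surgery and the first 24 hours. Cryoprecipitate is not listed.
- **Test** (Statistical Methods): "Analyses of the safety outcomes in Aims 1 and 2 will be noninferiority assessments, and so 1-tailed". For Aim 2, "Noninferiority of HES to albumin will be assessed for each outcome at the 0.025 level using a noninferiority delta of 15% of the mean", and "We will claim noninferiority of HES to standard within a set if noninferiority is shown on all of the variables in a set".

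**The concern.** Aim 2 asks whether HES harms coagulation and platelet function, and the background section gives that suspicion as its reason. If the suspicion is right, HES patients would be expected to meet the transfusion criteria more often. Components then raise the platelet count or shorten clotting times before the first study sample is drawn. The comparison becomes one of fluid plus corrective treatment, while the claim reads as one about the fluid. For any variable that the component corrects, the bias runs toward no difference. In a noninferiority test of safety that is the anti-conservative direction.

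**Working it through.** **1. Order of events.** Study fluid after bypass → components permitted in the same period → samples around ICU arrival and at 24 hours. Table 1 marks thromboelastography and aggregometry in the operating room, but the outcome text names only baseline, ICU arrival and 24 hours, so that mark is the baseline. No study sample is scheduled between study fluid and transfusion.

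**2. Variables affected.** The coagulation set has 7 variables (PT, aPTT, R, K, angle, MA, LY30). The platelet set has 4 (count and three aggregation tests). Of these 7 + 4 = 11, the transfusion section names 3: platelet count, PT and aPTT. The other 8 are not named, but they too are measured after any transfusion.

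**3. Handling in the analysis.** The mixed model adjusts for the baseline value and imbalanced baseline variables. The named sensitivity analysis concerns the primary outcome and covers bypass time, surgery length and hypothermia. The worst/best assignment under Missing data applies only to missing values. None of these addresses a value observed after transfusion.

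**4. Size, as an illustration for platelet count.** The plan gives no figure to reproduce: it has no platelet level, transfusion rate, increment or power for Aim 2.

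From the plan: one-sided 0.025, 15% margin, maximum 130 analysed. Assumed: 65 per arm (1:1), margin read as a ratio of 0.85, log-normal counts with CV 30%, control geometric mean 110-150, 50-100% of patients below 100 transfused, and a gain of 30-40 in each.

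Formulas:
- Log-scale SD: σ = √ln(1 + 0.30²) = 0.2936.
- Without transfusion: SE = 0.2936 × √(2/65) = 0.0515.
- P(pass) = Φ[(ln ratio − ln 0.85)/SE − 1.96].

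Without transfusion:
- True ratio 0.85: Φ(−1.96) = 2.5%.
- True ratio 0.80: Φ(−0.0606/0.0515 − 1.96) = Φ(−3.14) = 0.1%.

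With transfusion, one case in full (control 130, true ratio 0.85, all below 100 transfused, gain 30):
- Below 100 on albumin: Φ[(ln 100 − ln 130)/0.2936] = 19%.
- Below 100 on HES (geometric mean 110.5): Φ[(ln 100 − ln 110.5)/0.2936] = 37%.
- Simulating the measured counts gives a ratio of 0.902 and an SE of 0.0363. The SE falls because the low tail is lifted.
- P(pass) = Φ(0.0594/0.0363 − 1.96) = Φ(−0.32) = 37%.

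All cases (ranges are for gains of 30 to 40):

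| Control geometric mean | Share of those below 100 transfused | Transfused at true ratio 0.85, albumin / HES | Pass, true ratio 0.85 | Pass, true ratio 0.80 |
|---|---|---|---|---|
| 110 | half | 19% / 30% | 14-20% | 2-4% |
| 110 | all | 37% / 59% | 73-95% | 37-82% |
| 130 | half | 9% / 18% | 10-13% | 1-2% |
| 130 | all | 19% / 37% | 37-60% | 11-33% |
| 150 | half | 4% / 10% | 6-7% | 0.4-0.7% |
| 150 | all | 8% / 20% | 14-22% | 2-5% |

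A second simulation (log-SD 0.25, margin as a ratio of 1.15, gains of 20-40, otherwise the same ranges) gave about 5-97% at the margin.

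The illustration uses one variable at one time point. The plan's model adjusts for baseline and includes the 24-hour value, so these figures show direction and possible range, not a forecast.

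**The case against.** A reader might infer that transfusion will hide HES coagulopathy and that HES will then be declared safe. The documents do not support that, for five reasons.

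- **All variables in a set must pass.** A deficit that components leave uncorrected in any one thromboelastography or aggregation variable still blocks its set. Nothing in the documents shows that those 8 variables would normalise. Equally, nothing ensures that one stays abnormal, so the protection is real but not guaranteed.
- **The transfusion data are not ignored.** Component use and chest tube output are reported by group. The Secondary Aim 2 text bases safety conclusions on descriptive results alongside the tests, and conclusions beyond the primary outcome are called more exploratory. This stands. What is missing is a test, margin or rule saying what happens to a noninferiority claim if HES patients received more components.
- **Transfusion is not simply triggered by the outcome values.** The rule is permissive, and bleeding and clinician judgment also count. The words "elevated prothrombin time, or elevated activated partial thromboplastin time" can be read either as grounds for plasma or as findings that should be absent. That sentence must be clarified.
- **Clinicians are blinded.** That makes the criteria the same in both arms, but not how often they are met.
- **The larger percentages need extreme inputs.** With half of those below 100 transfused, a true 20% fall passes in about 0.4-4% of trials, and at the margin about 6-20%. This stands, and is why only the full range should be quoted.

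**Conclusion.** The gap is real and worth closing. All post-baseline Aim 2 values follow possible corrective transfusion, the analysis has no provision for it, and the bias for corrected variables favours noninferiority. Its size cannot be derived from the documents. Under the stated assumptions for platelet count alone, false noninferiority at the margin is about 6-95% instead of 2.5%, and for a true 20% fall about 0.4-82% instead of 0.1%. These are pass rates for one variable, not for a set, and they do not show that HES would be judged safe. Because Aim 2 is secondary and labelled more exploratory, the point bears on how its claim may be read and does not touch the primary NGAL analysis.

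**What to change.** Leave transfusion practice unchanged and amend the analysis and data collection.

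1. Make any platelet, plasma or cryoprecipitate transfusion from the start of study fluid to 24 hours a named Aim 2 outcome, reported with its risk difference and confidence interval. State that a set-level noninferiority claim is interpreted jointly with it, and is not read as evidence of safety if component use is higher with HES.
2. Add cryoprecipitate, and the time of each transfusion relative to the samples, to the collected data. Clarify the plasma sentence on PT and aPTT.
3. Pre-specify a supportive sensitivity analysis, not a condition of the claim, for values measured after transfusion. Limit it to variables that the given component would affect. An unfavourable-value imputation on the original scale keeps the 15% margin usable. A worst-rank comparison would have no such margin, and applied to every variable it would count a platelet transfusion against PT.

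Cost: SAP wording, one new data field and transfusion times; the other amounts are already collected. The Aim 2 claim becomes somewhat harder to make, and transfusions for surgical or bypass-related causes add noise.
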